estradiol will improve vaginal symptoms and modify the genital tract aging phenotype. HIV+ women who agree to participate in the trial will have 3 additional study visits: randomization (Visit 3), 6 weeks after randomization (Visit 4) and 12 weeks after randomization (Visit 5). HIV- women can only participate in Aim 1 and will have 2 study visits. HIV+ women can elect to participate in Aim 1 and/or Aim 2 (2 study visits if only Aim 1 is completed; 4 study visits if only Aim 2 is completed; 5 visits if both Aims 1 and 2 are completed).

Inclusion criteria for Aim 1 (first 2 study visits):

- HIV infection or HIV negative
- Females aged 45-70
- Menopause defined by having no menstrual periods for 12 consecutive months, confirmed with serum follicle-stimulating hormone (FSH) level >40 IU/ml and serum estradiol level <20 pg/ml

In the second part of the study (Aim 2), we propose a pilot randomized clinical trial nested in the Bronx WIHS in 50 menopausal WLWH with symptomatic vaginal atrophy to assess the impact of 12 weeks of a topical low-dose estradiol vaginal tablet (Vagifem® 10 µg) on symptoms of atrophy and measures of the vaginal microbiome. Participants will be randomized 1:1 to estradiol (n=25) or no therapy (n=25) and will be followed for 12 weeks. The dosing of Vagifem® will be 1 tablet inserted using a plastic applicator (similar to a tampon) in the vagina daily for 2 weeks followed by 1 tablet inserted twice weekly (i.e., Tuesday and Friday). If we find benefit among women assigned to the estradiol arm, participants randomized to the no therapy arm will be offered vaginal estradiol treatment at the end of the study by their primary care doctor. If participants assigned to Vagifem are symptomatic beyond the 12-week study period and wish to continue Vagifem®, it can be prescribed by their primary care physician. Women will have 3 visits before (Visits 1, 2 and 3) and 2 visits following Vagifem® treatment (Visits 4 and 5). Adherence to Vagifem will be assessed with the use of participant diaries of Vagifem use and counting of used Vagifem applicators.

Inclusion criteria for Aim 2 (randomized clinical trial for HIV+ participants only):

- HIV infection
- Females aged 45-70
- Menopause defined by having no menstrual periods for 12 consecutive months, confirmed with serum follicle-stimulating hormone (FSH) level >40 IU/ml and serum estradiol level <20 pg/ml

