a dichotomous variable (e.g. age 45-55 vs. 56-70) to examine the magnitude of difference between younger and older HIV+ and HIV- menopausal participants. We have chosen the age cut offs above given the significant differences observed in the taxonomic composition of the microbiome in pilot studies when comparing HIV+ menopausal participants in these age ranges and the distribution of eligible participants in WIHS. We will adjust the regression analysis for important covariates including years since menopause, time since HIV diagnosis, HIV plasma viral load, CD4 count, ART use, and HSV-2 serostatus. Both raw p values and the false discovery rate (FDR) according to Benjamini and Hochberg will be examined. To limit the false positive rate in our analysis of secondary outcomes, an arbitrary cutoff of 0.05 for FDR will be used.

Power Considerations: We estimated the power of the proposed study using software PASS (Power and Sample Size Analysis, version 11). Given the sample size of 50 HIV- and 50 HIV+ menopausal participants, we will have >80% power for the minimal detectable difference of 0.6SD and 0.9SD between HIV (or age) group with the significance level of 0.05 and 0.0005 (a conservative Bonferroni correction for 100 independent tests). Data from preliminary studies in our lab investigating the impact of menopause and HIV status on the vaginal microbiome indicated 51 HIV+ menopausal participants had a significantly lower relative abundance of lactobacillus species of 7.3% compared to 23% for 19 HIV- menopausal participants, equivalent to about 0.8SD change. Further when comparing upper and lower age ranges of HIV+ menopausal participants, HIV+ participants age 56-70 (n=28) had significantly lower relative proportions of *L. iners* 7.4% compared to 44.7% in HIV+ menopausal participants aged 47-55.9 (n=23), equivalent to about 1.2SD change. Based on the preliminary data, we are confident that this study will have excellent power to detect effects of age and HIV.

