Aim 2: The primary outcomes are clinical symptoms measured by most bothersome symptom of vaginal atrophy and changes in the vaginal microbiome, specifically the relative abundance of protective lactobacillus species *L. crispatus* as measured by Illumina MiSeq and quantities of protective lactobacilli species (*L. crispatus*, *L. jensenii* and *L. gasseri*) as measured by qPCR between baseline and 6 and 12 weeks within individual participants and between participants randomized to estradiol vs. no drug at baseline, 6 and 12 weeks. The 12-week time frame was chosen as this was the endpoint utilized in several clinical trials demonstrating Vagifem efficacy and is recommended in FDA guidelines^{22,43}. The secondary outcomes are changes relative abundance and quantities of specific BV associated bacteria and levels CVL cytokine/chemokines between baseline, 6 and 12 weeks. Exploratory outcomes are the quantities and composition of Ig coated bacteria and levels of HIV-1 in the genital tract. Spearman's correlation coefficients (SCC) will be calculated to evaluate associations between pairs of quantitative outcome variables and covariates, such as levels of protective lactobacilli species and MBS of atrophy, quantity of Ig coated bacteria, inflammatory mediators, CVL HIV-1 RNA, levels of estradiol in the blood. Linear mixed effects models or generalized linear mixed models will be used to examine effects of time and estradiol use on outcomes (bacterial communities, vaginal bacterial quantities, symptoms) after adjustment for factors such as ART, duration of HIV, plasma viral load, and CD4+ T cell count. We will also address the variability of the microbiome and inflammatory mediators over time in the absence of an intervention by comparing these measures at the screening (Visit 2) and enrollment visits (Visit 3).

Power Considerations: We have increased our sample size and added randomization for this clinical trial based on feedback from the NIH reviewers. If we assume an attrition rate of 15%, a sample of 50 HIV+ women randomized to estradiol (Vagifem) vs. no treatment will have >80%

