power for the minimal detectable difference in lactobacilli of 0.85 SD and 1.4 SD with the significance level of 0.05 and 0.0005 (a conservative Bonferroni correction for 100 independent tests), respectively, at 12 weeks post treatment. Although data is lacking in HIV+ women treated with Vagifem, a previous study with a smaller sample size (30 HIV-) investigating the use of low dose (0.3mg) oral conjugated estrogens for treatment of vaginal atrophy in demonstrated a significant increase in the relative abundance of Lactobacillus from 11.2% to 71% ($p<0.0001$) comparing baseline to 4 weeks estrogen treatment. Further the vaginal symptom score decreased from 3.93 vs. 1.00 ($p<0.0001$) at the same time points⁴¹, suggesting this proposed study may have adequate power for detecting a realistic difference of candidate Lactobacillus and symptom score. It should be noted that this is a pilot study and as such we acknowledge that it may be underpowered for testing interaction effects of time and estradiol use. However, the goal of the study is to determine an effect size of topical estradiol in planning for a future large-scale randomized controlled trial.

References

4. Wing EJ. HIV and aging. *International journal of infectious diseases : IJID : official publication of the International Society for Infectious Diseases*. 2016;53:61-68.

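### Aim 2's stated power of more than 80% at 0.85 SD is slightly overstated at the plan's own 15% attrition: about 77% by two-sided t-test, just under 80% by normal approximation

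*Combined protocol and SAP*

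**What the plan says.** Section 4 (Objectives and Study Design) sets the arm sizes for Aim 2: "Participants will be randomized 1:1 to estradiol (n=25) or no therapy (n=25) and will be followed for 12 weeks". Section 10 (Data analysis and sample size), in the Aim 2 power paragraph, states: "If we assume an attrition rate of 15%, a sample of 50 HIV+ women randomized to estradiol (Vagifem) vs. no treatment will have >80" (percent). The differences follow as a "minimal detectable difference in lactobacilli of 0.85 SD and 1.4 SD with the significance level of 0.05 and 0.0005". The smaller alpha is 0.05 divided by 100 tests, and the comparison is at 12 weeks.

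That paragraph names no test, no sidedness and no number of completers per arm. The software appears only under Aim 1 ("We estimated the power of the proposed study using software PASS"), without the procedure used. The planned Aim 2 analysis is a covariate-adjusted linear or generalized linear mixed model. The paragraph also says that the trial is a pilot and that "the goal of the study is to determine an effect size of topical estradiol".

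**The concern.** Every input needed to check the statement is printed next to it: 50 women, equal allocation, 15% loss, two differences in SD units and two alpha levels. With those inputs the 0.85 SD claim does not come out above 80%.

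What is at stake is the accuracy of one sentence. A reader who uses the printed detectable difference to judge what this pilot can show, or to plan the later trial, would take it as slightly smaller than it is. Because the test and the number of completers are not given, that reader also cannot tell how the figure was obtained.

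**Working it through.** **Inputs.** From section 4: 25 per arm. From section 10, Aim 2: 15% attrition; 0.85 SD at alpha 0.05; 1.4 SD at alpha 0.0005; power above 80%. Assumptions not in the plan: two-sided testing, an unadjusted two-group comparison of completers at 12 weeks, and loss spread evenly over the arms.

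**Completers.** 50 × 0.85 = 42.5, so 42 (21/21) or 43 (21/22).

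**Formulas.** With a difference of d in SD units, δ = d × √(n1·n2/(n1+n2)).
- Two-sided t-test: power = P(noncentral t with n1+n2−2 df and noncentrality δ exceeds t(1−α/2)).
- Two-sided normal approximation: power = Φ(δ − z(1−α/2)), with z = 1.960 at alpha 0.05 and 3.481 at alpha 0.0005.
- The opposite tail is negligible in both.

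**Worked case, 21/21.** √(441/42) = 3.240.
- 0.85 SD: δ = 2.754. Against t = 2.021 (40 df), power is 0.767. By normal approximation, Φ(2.754 − 1.960) = Φ(0.794) = 0.787.
- 1.4 SD: δ = 4.537. Against t = 3.788, power is 0.762. By normal approximation, Φ(4.537 − 3.481) = Φ(1.056) = 0.854.

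**All cases.**

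| Completers | Loss | 0.85 SD, t | 0.85 SD, normal | 1.4 SD, t | 1.4 SD, normal |
|---|---|---|---|---|---|
| 25/25 | 0% | 0.838 | 0.852 | 0.876 | 0.929 |
| 23/23 | 8% | 0.805 | 0.822 | 0.826 | 0.897 |
| 22/22 | 12% | 0.786 | 0.805 | 0.796 | 0.877 |
| 21/22 | 14% | 0.776 | 0.796 | 0.779 | 0.866 |
| 21/21 | 16% | 0.767 | 0.787 | 0.762 | 0.854 |

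The 15% assumption lies between the last two rows. Simulating the two-sided t-test (400,000 replicates per case) at 21/21 and 21/22 gave 0.767 and 0.777 for 0.85 SD, and 0.761 and 0.779 for 1.4 SD.

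**Difference detectable with 80% power.**

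| Completers | t, alpha 0.05 | t, alpha 0.0005 | normal, alpha 0.05 | normal, alpha 0.0005 |
|---|---|---|---|---|
| 21/22 | 0.875 | 1.424 | 0.855 | 1.319 |
| 21/21 | 0.886 | 1.444 | 0.865 | 1.334 |

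**Reproducing the plan's pair.** None of the methods tried returns both 0.85 and 1.4 at 15% loss. The normal approximation at 21/22 gives 0.855 (0.8547 before rounding), which can print as 0.85, but its companion is 1.32. A one-sided t-test at 21/21 has more than 80% power for both (0.856 and 0.826), but its detectable pair is 0.78 and 1.37. A two-sided t-test at 22/22 comes near, with 0.865 and 1.405, but 22/22 is 12% loss.

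**Aim 1 as a cross-check.** There the plan gives a "minimal detectable difference of 0.6SD and 0.9SD between HIV (or age) group with the significance level of 0.05 and 0.0005" with 50 per group. Power is 0.844 and 0.811 by t-test, and 0.851 and 0.846 by normal approximation. The Aim 1 statement holds under both, so it does not show which method was used.

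**The case against.** The strongest reply is that any shortfall depends on a test that the plan never names. By normal approximation at 21/22, the 80% detectable difference rounds to 0.85 SD, power is 79.6%, and 1.4 SD clears 80% easily. A one-sided test clears both. The planned analysis is an adjusted mixed model with repeated pre-treatment samples, which can be more efficient than a t-test on completers. If adjustment for baseline is approximated by dividing d by √(1 − r²), an assumed correlation r of 0.3 gives 80.4% and 81.9% at 21/21, while r of 0.2 gives 78.3% and 78.7%.

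Much of this stands. The 1.4 SD figure cannot be called wrong, and about 77% is conditional on a t-test. The rest does not restore the 0.85 SD claim. The sentence says above 80%, and 79.6% is not. Treating completers as 22 per arm replaces the stated attrition with 12%. One-sided testing is stated nowhere and does not give the printed pair. The gain from adjustment needs a correlation that the plan does not supply.

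A reader might go further in three ways, none of which the documents support:
- That attrition was ignored. Without loss, t-test power would be 83.8% and 87.6%, and the printed differences are larger than 25 per arm would need, so some allowance was evidently made.
- That the authors worked with 22 per arm and rounded down. The near match is suggestive, but nothing in the text shows their working.
- That the sample should grow. By t-test, 80% power needs 23 completers per arm, or 46/0.85 = 54.1, so 55 randomized. But the stated purpose is to determine an effect size, and the plan already concedes that it may lack power for the time-by-estradiol interaction.

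**Conclusion.** The concern holds for 0.85 SD at alpha 0.05. At the stated 15% attrition, power falls below the stated level by 2.4 to 3.3 points with a two-sided t-test and by 0.4 to 1.3 points with the normal approximation. This rests on two-sided testing, an unadjusted comparison and equal loss across arms.

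For 1.4 SD at alpha 0.0005 the answer depends on the method: 2.1 to 3.8 points short by t-test, 5.4 to 6.6 points above by normal approximation. To say that both power figures are wrong would go beyond the documents.

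This is a small reporting inaccuracy. It does not undermine the design of a pilot with this aim.

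**What to change.** Restate the power sentence in one of two ways.

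1. Keep 80% power and change the differences, for example: *with 15% attrition (about 21 completers per arm), an unadjusted two-sided two-sample t-test has 80% power for about 0.88 to 0.89 SD at alpha 0.05 and about 1.42 to 1.44 SD at alpha 0.0005.*
2. Keep 0.85 SD and give its power as about 77% by two-sided t-test (79% to 80% by normal approximation). If 1.4 SD is kept too, give its power under the same named method.

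Either way, name the test, the sidedness and the completers per arm. If the authors rely on baseline adjustment, they should state the assumed correlation and its source. The cost is one sentence, with no change to sample size, design, analysis or conduct.
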